1 BACKGROUND

Endocrine therapy in breast cancer

Endocrine therapy is an established treatment for hormone receptor-positive breast cancer ¹⁻³. Endocrine therapy can cause significant side effects with deterioration in quality of life⁴. Tamoxifen and aromatase inhibitors (e.g. letrozole, anastrozole and exemestane) share common side effects such as hot flashes, arthralgia/joint stiffness, insomnia, weight gain, mood changes, gastrointestinal symptoms, and skin and vaginal dryness. In addition, while tamoxifen carries a higher risk of vaginal bleeding or discharge, thromboembolic events and uterine cancer, the aromatase inhibitors are associated with an increased risk of cardiovascular events, osteoporosis and bone fractures⁵⁻⁷.

Non-persistance or non-compliance to endocrine therapy

The side effects of all forms of endocrine therapy are well recognised and can lead to treatment non-persistance or non-compliance. Compliance is defined as the degree or extent of conformity to the recommended administration by the provider, whereas persistence refers to the act of continuing treatment for a certain prescribed duration⁸. A systematic review of adjuvant endocrine treatment found that 41 to 72% of patients did not take the correct dosage at the prescribed frequency and 31 to 73% discontinue endocrine therapy⁹. Treatment adherence is especially important in breast cancer, as early cessation or reduced compliance to hormonal therapy are associated with reduced disease-free survival and increased mortality^{10,11}. In order to maximize adherence, strategies have been used to mitigate these side effects. Regarding the hot flashes,

patients may benefit from lifestyle changes such as exercising and avoiding caffeine, alcohol as well as smoking^{12,13}. Many nonhormonal pharmacotherapies have been used to try controlling vasomotor symptoms including selective serotonin reuptake inhibitors/serotonin-norepinephrine reuptake inhibitors antidepressants, gabapentin and oxybutynin¹³. Most recently the Oncology Nursing Society published guidelines for cancer related hot flashes suggesting the use of sertraline, fluoxetine, escitalopram, duloxetine or clonidine. However, these pharmacologic strategies to control endocrine therapy side effects present their own array of potential side effects and often not well tolerated themselves¹⁴.

Chronotherapy

Chronotherapy, also called chronotherapeutics, is defined as the administration of a medication in coordination with the circadian rhythm in order to minimize side effects and yield a greater efficacy¹⁵. While this concept is based on a strong mechanistic foundation involving xenobiotic metabolism and detoxification of drugs, only a few clinical trials, mainly for neurologic, behavioral and psychiatric conditions, factored in circadian timing¹⁵. Recently, a study demonstrated that the time of day at which antihypertensives are taken can impact their effectiveness¹⁶. In breast cancer, one randomized trial evaluating the optimal time for administering vinorelbine showed a non-statistical benefit for the incidence of grade 3-4 neutropenia when administered at 21:00 and grade 3-4 gastrointestinal toxicity when administered at 10:30¹⁷. Furthermore, there is some evidence suggesting that the adherence to drugs might be greater in the morning as compared to the evening¹⁸. Many online forums exist with breast cancer patients seeking insight on the time of day (i.e. morning vs evening) to take their endocrine therapy¹⁹. In

our practice, we often see doctors and nurses using a trial and error method to help patients determine the best time of day at which to take their endocrine therapy to try reducing these side effects, with anecdotal success. Even though this clinical practice is not evidence-based, there is increasing molecular evidence suggesting an interplay between circulating estradiol and expression of circadian clock genes that may support this practice²⁰.

Evidence from a recent systematic review

Our team recently conducted a systematic review to assess the evidence currently available regarding the circadian administration of endocrine therapy in terms of side effects, quality of life and disease-free survival in breast cancer patients. Ovid Medline, EMBASE, and the Cochrane Central Register of Controlled Trials were searched from 1947 to August 2020 for relevant randomized control trials or prospective cohort studies and off 361 unique citations identified, 0 studies met eligibility criteria.

Ongoing clinical trials

A search of the ClinicalTrials.gov database to identify all active registered trials looking at the best “time-of-day” administration of endocrine therapy was done on December 18, 2020. No registered studies on this specific question were found.

Clinical trial rationale

Although optimal time-finding trials have been conducted in other medical fields, none have been undertaken for hormonal therapy in breast cancer^{15,20}. Patients and clinicians are relying on a trial and error approach to determine the best time of treatment with the goal of reducing side effects and improving QoL and adherence. However, this practice is neither evidence-based nor standard of care. Therefore, conducting the **world's first prospective randomized clinical trial** to evaluate the dose timing (morning versus evening) of endocrine therapy and its effects on tolerability and adherence is warranted and needed.

Clinical trial significance

Nonadherence and discontinuation of endocrine therapy has been an important clinical issue given its high prevalence and its negative impact on breast cancer mortality^{11,21}. New non-pharmacological interventions to improve adherence and side effect profile of endocrine therapy are critically needed¹¹. Changing the time of the day at which a medication is taken is a new, simple, easy intervention that does not generate additional costs.

From a patient perspective, finding a new strategy to reduce side effects associated with endocrine therapy will improve the quality of life of thousands of Canadian women with breast cancer and will help increase their compliance to endocrine therapy. Optimizing adherence to endocrine therapy by changing the time of the day at which it is taken will have a positive impact on breast cancer outcomes. Furthermore, this will reduce indirect

cost related to breast cancer recurrence and the use of pharmacological interventions to reduce side effects.

1.1 Pragmatic trials

Since 2014 the Rethinking Clinical Trials (REaCT) has been operating across Canada with the specific aim of performing pragmatic trials when physicians do not know what the “best” treatment for patients is, and genuine uncertainty (“clinical equipoise”) exists. Currently the choice between taking endocrine therapy in the morning or evening depends more on choosing between different “standards” in their personal practice, using idiosyncratic decision-making processes, without the physician or the patient relying on an evidence-based option. Determining the optimal treatment timing remains an important medical issue for both patients and physicians.

This study will use robust methodology to allow comparisons of established standard of care treatment using the “integrated consent model” as part of a pragmatic clinical trial²². By integrating medical and clinical practices, physicians will be able to inform their patients about the RCT, through a typical conversation between the physician and patient, with oral informed consent. This clinical interaction would then be documented in the consult note, as ordinarily done in practice.

Pragmatic clinical trials are being given increased importance, as they commonly consist of comparative effectiveness research, thus comparing the safety and effectiveness of

diagnostic, therapeutic or delivery systems. Additionally, these studies have not only the ability to leverage patient data from electronic health records to increase sample size of trials at much lower costs, but also enabling major national and international initiatives to generate the data needed to improve care²². As such, the Integrated Consent Model is being increasingly used internationally to improve patient care^{22,23}. In fact, The Ottawa Hospital Cancer Centre is leading this program with over 3000 patients already enrolled on REACT trials at 15 Canadian Cancer Centres. These studies have shown excellent patient feedback with 97% of patients rating being 'completely satisfied' with the REaCT process.

Thus, we propose to perform a pragmatic, multicentre, open-label, randomized clinical trial to establish the optimal timing (morning vs evening) of administering endocrine therapy based on side effects and benefits in early stage breast cancer patients.

1.2 Central Hypothesis or Research Question

Hypothesis: We hypothesize that the dose timing (morning vs evening) of endocrine therapy will impact side effects and benefits as assessed using the validated Functional Assessment of Cancer Therapy-Endocrine Subscale (FACT-ES)^{24,25}.

2 OUTCOMES

2.1 Primary Outcome

- Endocrine toxicity and tolerability measured by the change in total FACT-ES score (a validated subscale of the FACIT measurement system) from baseline to 12 weeks following the beginning of endocrine therapy

2.2 Secondary Outcomes

- Endocrine toxicity and tolerability measured by the change in total score and individual items of FACT-ES from baseline to 4, 8, 12 and 52 weeks following the beginning of endocrine therapy
- Quality of life measured by the change in the total score and individual subscales of the validated Functional Assessment of Cancer Therapy for patients with a Breast cancer (FACT-B) questionnaire from baseline to 4, 8, 12 and 52 weeks following the beginning of endocrine therapy
- Rates of discontinuation, interruption and non-compliance (defined as patient taking less than 80% of the prescribed endocrine therapy) with initially prescribed endocrine therapy
- Cost-effectiveness: incremental cost-effectiveness ratios (cost per one quality-adjusted life year (QALY) gained

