5.2 Analysis Methods

Descriptive analysis: Baseline characteristics will be presented with means (continuous measures) or proportions (categorical or ordinal data) with 95% confidence intervals.

Intention-to-treat analysis: The primary analysis will be based on the intent-to-treat principle, thus, all participants who are randomized will be included in the final study analysis. The last observation carried forward method will be used to impute results for any patient who is lost to follow-up, or who does not have a FACT-ES score measured at the 12 week time point. This is a conservative approach to imputation, as it will likely result in smaller differences between groups than would actually be present (if there is an actual difference), under the assumption that increased effects will occur over time up to week 12. In addition, a per protocol analysis of the primary outcome measure will be conducted,

which will include only those patients who follow the intervention as prescribed in the protocol, and who complete both the baseline and 12 week FACT-ES score.

Analysis of primary and secondary outcomes: Dichotomous outcomes will be summarized according to proportions and 95% confidence intervals. Continuous outcomes will be summarized according to means and standard deviations or medians and interquartile ranges as appropriate. The primary analysis will be based on a logistic regression analysis with adjustment for stratification factors. Additional logistic and linear regression analyses will be performed with adjustment for stratum. Univariable comparisons between the intervention and control groups will be examined using a Chi-Squared test for dichotomous events, and a student's t-test for continuous measures. Non-parametric methods may be used in lieu of these tests as appropriate. All analyses will be supplemented with 95% confidence intervals where relevant.

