Health economic evaluation: We will perform a cost utility analysis alongside this pragmatic randomized controlled trial. Resource use and health utility values will be measured from the trial at the baseline and follow up interviews. We will derive health utility values from the European Quality of Life-5 Dimensions 5-level (EQ-5D-5L) questionnaire. We will develop a Markov model that represents lifetime experience of a patient cohort following her treatment option to predict the long-term prognosis of patients. The model will consist of multiple distinct states, representing breast cancer progression and relevant adverse events. It will also have the capacity to capture medication adherence. We will derive input parameters required for the model from the concurrent trial and the published literature. The results will be presented as incremental cost per quality-adjusted life year (QALY) gained and incremental cost per one endocrine toxicity

case averted. Both costs and outcome will be discounted at 1.5% annually. A series of sensitivity analysis will be undertaken to examine the effect of conducting a complete case only analysis and of varying input parameters. Parameter uncertainty will be assessed using Monte Carlo simulations with 10,000 simulations. The results of the simulations will be shown as effectiveness acceptability curves (CEACs), which represent the probability of a treatment being cost-effective to a range of potential threshold values that the health system may be willing to pay for an additional unit of effect. All analysis will be conducted using Microsoft Excel.

Compliance and loss to follow-up: Supportive analyses will be performed to better understand the impact of non-compliance, loss to follow-up and protocol violations. The primary analysis is clearly defined, and other analyses will be performed understanding the supportive and secondary nature of these results. Interpretation of results will be performed, clearly acknowledging the a priori defined primary analysis.

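### The cost-utility analysis collects baseline EQ-5D-5L utility but does not adjust the arm comparison of utilities or QALYs for it, which gives up precision at no saving.

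*Combined protocol and SAP*

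**What the plan says.** Section 2.2 lists the economic outcome as "Cost-effectiveness: incremental cost-effectiveness ratios (cost per one quality-adjusted life year (QALY) gained".

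The health economic part of section 5.2 describes how it is obtained:
- Timing of data: "Resource use and health utility values will be measured from the trial at the baseline and follow up interviews". Table 1 schedules EQ-5D-5L at baseline and at 4, 8, 12 and 52 weeks.
- Instrument: "We will derive health utility values from the European Quality of Life-5 Dimensions 5-level (EQ-5D-5L) questionnaire".
- Model: "We will develop a Markov model that represents lifetime experience of a patient cohort following her treatment option".
- Inputs: "We will derive input parameters required for the model from the concurrent trial and the published literature".
- Uncertainty: "Parameter uncertainty will be assessed using Monte Carlo simulations with 10,000 simulations", shown as acceptability curves over a range of thresholds. Sensitivity analyses cover complete cases and varied inputs.

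On covariates, section 5.2 adjusts the primary logistic regression for the stratification factors and then says: "Additional logistic and linear regression analyses will be performed with adjustment for stratum". Section 5.3 gives those factors as site, tamoxifen and chemotherapy. Baseline utility is neither a stratification factor nor a named covariate. The plan does not say whether trial utilities enter the model as raw levels, changes from baseline or adjusted means, or whether they are specific to each arm.

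**The concern.** A within-trial QALY is an area under the utility curve, so it accumulates levels. If the arms differ by chance in utility before treatment starts, part of that gap carries into the difference in QALYs. The FACT outcomes are defined as changes from baseline and so use the baseline score in some way; no equivalent step is stated for utility.

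Any QALY difference between morning and evening dosing may well be small compared with a chance baseline gap. What is at stake is the precision of one secondary outcome and, if the true difference is small, how often its estimate points the wrong way. Leaving the method open also allows a choice between adjusted and unadjusted results after the data are seen. The primary analysis is not affected.

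**Working it through.** **The plan's own figures.** The documents give no precision figure for the cost-utility outcome, so only the sample size can be reproduced. For 40% v 60%, two-sided alpha 0.05 and 80% power, the continuity-corrected formula gives 107 per arm, or 214 in total (97 per arm without the correction). Exact enumeration of Fisher's test at 107 per arm gives power 0.795. Then 214 × 1.10 = 235.4, which agrees with the target of 235.

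**Inputs for the check.**
- From the documents: 235 patients at 1:1 (118 v 117); utility at weeks 0, 4, 8, 12 and 52.
- Assumed, not in the documents: utility SD 0.15 (range 0.10 to 0.20), the same at each visit; equal correlation ρ = 0.6 between visits (range 0.5 to 0.7); true gain 0.01 QALY (0.02 also shown); complete data; trapezoid QALY over 52 weeks.

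**Step 1. Trapezoid weights.** 2/52, 4/52, 4/52, 22/52 and 20/52, that is 0.038, 0.077, 0.077, 0.423 and 0.385. The sum of squares is 0.340.

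**Step 2. Chance baseline gap.** SE = SD × √(1/118 + 1/117) = 0.15 × 0.1305 = 0.0196. The 95% range is ±1.96 × 0.0196 = ±0.038.

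**Step 3. Share of the gap that carries over.** Covariance of QALY with baseline, in units of SD²: ρ + (1 − ρ) × 0.038 = 0.6 + 0.4 × 0.038 = 0.615. About 62% of a baseline gap therefore appears in the expected unadjusted QALY difference.

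**Step 4. Variance with and without adjustment, in units of SD².**
- Unadjusted: ρ + (1 − ρ) × 0.340 = 0.6 + 0.136 = 0.736.
- Adjusted for baseline: 0.736 − 0.615² = 0.736 − 0.379 = 0.357.
- R² = 0.379/0.736 = 0.514, and the variance ratio is 1/(1 − 0.514) = 2.06.

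At ρ = 0.5, R² is 0.402 and the ratio 1.7; at ρ = 0.7, R² is 0.631 and the ratio 2.7. The ratio does not depend on the SD or on the true gain.

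**Step 5. Standard error of the QALY difference.**
- Unadjusted: 0.15 × √0.736 × 0.1305 = 0.0168.
- Adjusted: 0.15 × √0.357 × 0.1305 = 0.0117.

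**Step 6. Probability that the estimate has the wrong sign**, Φ(−gain/SE):

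| True gain | Unadjusted | Adjusted |
|---|---|---|
| 0.01 QALY | Φ(−0.596) = 27.6% | Φ(−0.855) = 19.6% |
| 0.02 QALY | Φ(−1.191) = 11.7% | Φ(−1.709) = 4.4% |

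For a gain of 0.01, the ranges over SD 0.10 to 0.20 and ρ 0.5 to 0.7 are 17% to 33% unadjusted and 8% to 27% adjusted.

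**Step 7. If changes from baseline were used instead of levels.** The variance would be 0.736 + 1 − 2 × 0.615 = 0.505 (unrounded inputs), which is 0.505/0.357 = 1.41 times the adjusted variance. The gain from regression adjustment is then smaller, but it remains.

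**The case against.** The strongest reply is that the cost-utility result comes from a lifetime Markov model and not from a one-year area under the curve. The model has states for progression and adverse events, can represent adherence, discounts at 1.5% and draws partly on the literature. If utilities attach to health states rather than to arms, the arms differ through transitions, toxicity and adherence, and a baseline gap in mean utility need not reach the result. This stands. The figures above illustrate only the part that uses arm-specific trial utilities, and the plan does not say how large that part is. It also follows that one cannot say the plan uses unadjusted levels: it is silent on the point, and that silence is the gap.

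A reader might infer that cost-effectiveness is to be reported as a bare ratio, so that a negative value could mean either dominant or dominated. The documents do not support that. Section 5.2 plans simulations and acceptability curves over a range of thresholds, and a probability of being cost-effective at each threshold separates the two cases. It also calls for 95% confidence intervals where relevant. The planned simulations do not cure imbalance, however: built on unadjusted arm means, they stay centred on the imbalanced estimate.

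A reader might also infer that incremental cost must lie near zero, because section 1 calls the change of timing an "easy intervention that does not generate additional costs". That describes the act of changing the dosing time. The same part of section 1 goes on to expect savings in indirect cost, from recurrence and from drugs used against side effects. Near-equal costs are therefore not established.

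**Conclusion.** The point holds as a free improvement to one secondary outcome. Baseline utility is collected, no adjustment for it is stated, and where arm-specific trial utilities are used the omission costs precision. Under the stated assumptions the variance of the one-year QALY difference is about twice what it needs to be (ratio 2.1; 1.7 to 2.7 for correlations 0.5 to 0.7), and the wrong-sign probability for a 0.01 QALY gain is about 28% instead of 20%. The SD, correlation and gain are all assumed. The wrong-sign figures depend on all three; the variance ratio depends only on the correlation and the visit schedule.

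Two stronger readings are not supported. Under randomisation the unadjusted estimate is not biased on average; imbalance is extra variance, or bias only conditional on the gap observed. Nor is it shown that imbalance would decide which arm is called cost-effective, since the plan states no threshold or decision rule and the weight of trial utilities in the model is unknown.

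**What to change.** In the health economic part of section 5.2:
- State whether trial utilities are arm-specific, and in what form they enter the Markov model.
- Estimate the 52-week utility or QALY difference by regression on arm, with baseline EQ-5D-5L utility and the stratification factors as covariates.
- Carry the adjusted estimates and their uncertainty into any arm-specific model inputs, the 10,000 simulations and the acceptability curves.

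Reporting incremental net monetary benefit with an interval beside the ratio is an optional choice of presentation.

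The cost is a few sentences, written before outcome data are examined. No new data, patients or visits are needed, and the simulations are already planned.

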2.3 Exploratory analyses

- Comparing rates of non-persistence or non-compliance with patient age, tumour stage, chemotherapy use, type of endocrine therapy

2.4 Interim analysis / feasibility

An interim analysis will be performed after the first year of study initiation, focusing on recruitment and safety aspects only. The study will be stopped if recruitment is <80 patients (~40% of total target) after one year or if considerable unanticipated safety issues arise.

3 STUDY DESIGN

The study schema is shown in Figure 1. Eligible patients with hormone receptor positive breast cancer who will receive adjuvant endocrine therapy will be eligible for this study. Patients will be consented either by their treating medical oncologist or a member of their circle of care. Consenting patients will be randomized to one of two arms:

Arm A: Morning administration of endocrine therapy defined as, within one hour of the patient wake up time.

or

Arm B: Evening administration of endocrine therapy defined as, within one hour of the patient bed time.

There will be no study mandated change in either the type of endocrine therapy. Endocrine therapy can be started either before, prior or after radiation therapy prescribed, as per patients' choice.

Patients will be approached by their medical oncologists during routine clinic visits. In order to ensure trial findings are applicable to the broadest population possible, eligibility

criteria will be pragmatic. Patients will be assessed either as per their usual clinic visits, or as the study does not involve additional clinic visits, study questionnaires will be completed via electronic link sent via email. The questionnaires will be built into the electronic database developed by the Ottawa Methods Centre and patients will receive a secure electronic link to complete the questionnaires at the required study timepoints. If patients do not have access to a computer/internet, they can request to receive paper copies in the clinic or by mail.

Outcomes will be measured at:

- Baseline (prior to start endocrine therapy)
- 4 weeks (\pm 1 week) after the start of endocrine therapy
- 8 weeks (\pm 1 week) after the start of endocrine therapy
- 12 weeks (\pm 2 week) after the start of endocrine therapy
- 52 weeks (\pm 2 week) after the start of endocrine therapy

The study calendar is shown in Table 1.

